#### **10.5 Clinical Laboratory Assessments and Other Abnormal Assessments as Adverse Events and Serious Adverse Events**

It is the responsibility of the investigator to assess the clinical significance of all abnormal laboratory values as defined by the list of reference ranges from the local laboratory. In some

cases, significant change in laboratory values within the normal range may require similar assessment.

An abnormal value that is not already associated with an AE is to be recorded as an AE only if one of the following criteria is met:

- It resulted in treatment modification (reduction of dose, interruption of dosing, or permanent discontinuation of study drug)
- It required intervention/management
- It is suggestive of organ toxicity
- The investigator considers it to be clinically significant

## **10.6 Pregnancy or Drug Exposure during Pregnancy**

If a patient becomes pregnant during the course of the study, study drug dosing should be held immediately.

Pregnancy is not considered to be an AE or SAE; however, all pregnancies occurring during study participation or within 6 months of last dosing must be reported to the sponsor using the Clinical Pregnancy Report form within the same timelines as for as SAE.

All pregnancies should be followed through to outcome whenever possible. Once the outcome of a pregnancy is known, the Clinical Pregnancy Outcome Report form should be completed and submitted to the sponsor.

AEs, SAEs, or AESIs that occur during pregnancy will be assessed and processed according to the AE or SAE/AESI processes using the appropriate AE or SAE/AESI forms.

## **10.7 Recording of Adverse Events, Serious Adverse Events, and Adverse Events of Special Interest**

As of the implementation of Amendment 5, only SAEs/AESIs will be fully documented on the appropriate eCRF. For each SAE/AESI, the investigator must provide duration (start and end dates or ongoing), intensity, relationship to study drug, and indicate whether specific action or therapy was required.

Any SAE/AESI that occurs after the first dose of study drug until 28 days after last dose of study drug administration will be collected, documented and reported to the sponsor by the investigator according to the specific definitions and instructions detailed within this protocol, whether dosing has occurred or not. In addition, any AE/SAE that occurs after informed consent is obtained and is deemed related to a screening procedure for the study should also be reported on the AE eCRF and, if applicable, the SAE report form. Events that occur after signing of informed consent but prior to initiation of study drug, unless due to a protocol-mandated procedure, should be recorded on the Medical History eCRF. In order to avoid vague, ambiguous, or colloquial expressions, the AE should be recorded in standard medical terminology rather than the patient's own words. Whenever possible, the investigator should combine signs and symptoms that

constitute a single disease entity or syndrome into a final diagnosis. For example, fever, cough, and shortness of breath may be reported as pneumonia, if that is a reasonable diagnosis.

All SAEs/AESIs that occur during the study or within 28 days after receiving the last dose of study drug, regardless of relationship to study drug, must be reported to the sponsor/designated safety contact immediately (i.e., within 24 hours of the investigator's knowledge of the event). This should be done by faxing or emailing the completed SAE/AESI report to the sponsor/designee contact provided on the SAE/AESI report form. After the 28-day window after treatment discontinuation, only SAEs assessed as related to study drug and all AESIs, irrespective of causality, should be reported. If a patient is determined to be a screen failure, no further AEs/SAEs are required to be reported once that determination has been made, with the exception of AEs/SAEs deemed related to a protocol-specified procedure. Information on the follow-up of AEs, SAEs, and AESIs is provided in [Section 10.7.4](#).

### ***10.7.1 Intensity of Adverse Events***

Severity refers to the intensity of an AE. The severity of each AE will be categorized using the NCI-CTCAE, v4.03.

For any term that is not specifically listed in the CTCAE, intensity should be assigned a grade of 1-5 using the following CTCAE guidelines:

- Mild (Grade 1): mild or asymptomatic symptoms; clinical or diagnostic observations only; intervention not indicated
- Moderate (Grade 2): limiting age-appropriate instrumental activities of daily living; minimal, local or noninvasive intervention indicated
- Severe (Grade 3): limiting self-care activities of daily living; hospitalization indicated
- Life threatening (Grade 4): life-threatening consequences; urgent intervention indicated
- Fatal (Grade 5): results in death

### ***10.7.2 Causal Relationship of Adverse Events to Study Drug***

Medical judgment should be used to determine the cause of the AE considering all relevant factors such as, but not limited to, the disease under study, concurrent disease, concomitant medication, relevant history, pattern of the AE, temporal relationship to the study medication, dechallenge or rechallenge with the study drug.

Not Related To Study Drug	An AE that is clearly due to extraneous causes (eg, concurrent disease, concomitant medication, disease under study, etc.) An AE that does not follow a reasonable temporal sequence from administration of the study drug. An AE that does not follow a known pattern of response to study drug. An AE that does not reappear or worsen when study drug is restarted. An AE for which an alternative explanation is likely, but not clearly identifiable.
---------------------------	--

Related to Study Drug	An AE that is difficult to assign to alternative causes. An AE that follows a strong or reasonable temporal sequence from administration of study drug. An AE that could not be reasonably explained by the patient's clinical state, concurrent disease, or other concomitant therapy administered to the patient. An AE that follows a known response pattern to study drug. An AE that is confirmed with a positive rechallenge or supporting laboratory data.
-----------------------	---

### 10.7.3 Outcome

The investigator will record the outcome for each AE according to the following criteria:

- Recovered/Resolved
- Recovered/Resolved with sequelae
- Improved
- Ongoing
- Death
- Unknown/Lost to follow-up

### 10.7.4 Follow-up of Adverse Events, Serious Adverse Events, and Adverse Events of Special Interest

All AEs (including SAEs and AESIs) occurring during the study are to be followed up in accordance with good medical practice until resolved; judged no longer clinically significant; or, if a chronic condition, until fully characterized until 28 days after the last dose of study treatment. Any SAE/AESI must be followed until the event has resolved, the condition has stabilized, or the patient is lost to follow up. If the patient is lost to follow-up with an ongoing SAE/AESI, this should be captured accordingly on a follow-up SAE/AESI report.

## 10.8 Regulatory Aspects of Adverse Event Reporting

All SAEs and AESIs, irrespective of relationship to study treatment, as well as all pregnancies, must be reported to the sponsor's SAE designee **within 24 hours** of knowledge of the event, occurring during the study through 28 days after receiving the last dose of study treatment, according to the procedures below. After the 28-day specified window, SAEs considered to be treatment related and all AESIs, regardless of treatment relationship, should be reported if occurring. Pregnancies that occur within 6 months of the last dose of study drug should be reported. It is important that the investigator provide an assessment of relationship of the SAE/AESI to study treatment at the time of the initial report. The SAE/AESI Report form must be used for reporting SAEs/AESIs. The contact information for reporting of SAEs/AESIs can be found on the SAE/AESI Reporting Form and Pregnancy Report Forms.

Clovis Oncology, Inc. (Clovis Oncology), or its designee is responsible for submitting reports of AEs associated with the use of the drug that are both serious and unexpected to the Food and Drug Administration (FDA), according to 21 Code of Federal Regulations (CFR) 312.32; to the

European regulatory authorities according to the European Commission Clinical Trials Directive (2001/20/EC); and to other regulatory authorities, according to national law and/or local regulations. All investigators participating in ongoing clinical studies with the study medication will receive copies of these reports for prompt submission to their IRB or IEC. In accordance with the European Commission Clinical Trials Directive (2001/20/EC), Clovis Oncology or its designee will notify the relevant ethics committees in concerned member states of applicable suspected unexpected serious adverse reactions (SUSARs) as individual notifications or through periodic line listings.

Clovis Oncology or its designee will submit all safety updates and periodic reports to the regulatory authorities as required by applicable regulatory requirements.

## **10.9 Independent Data Monitoring Committee**

No formal efficacy interim analyses are planned.

An IDMC will be established to review safety and efficacy data in compliance with a prospective charter and will be involved until the primary endpoint has been met and the study unblinded. The IDMC will be comprised of medical oncologists with experience in treating women with ovarian cancer and a statistician, all of whom are not otherwise involved in the study as investigators. The IDMC responsibilities, authorities, and procedures will be documented in the IDMC charter, which will be endorsed and signed by the IDMC prior to the first data review meeting.

The IDMC will:

- Review safety and efficacy of rucaparib compared with placebo to ensure the study is beneficial to patients
- Ensure the study is conducted in a high quality manner
- Monitor the size of the tBRCA subgroup and the known gBRCA group

Following data review, the IDMC will recommend continuation, revision, or termination of the study and/or continuing or halting enrollment into a particular subgroup. The IDMC will meet at least semi-annually after sufficient data has been collected. The IDMC chairperson may convene formal IDMC meeting if there are safety concerns. The sponsor can also request an IDMC review of safety data.

## 11 STATISTICAL METHODS

### 11.1 Analysis Populations

The following analysis populations are defined for the study:

**Safety Table Population** – The safety population will consist of all patients who received at least one dose of protocol-specified treatment.

**Intent-to-treat (ITT) Population** – The ITT population will consist of all randomized patients.

### 11.2 Statistical Methods

#### 11.2.1 General Considerations

Variables registered on a continuous scale will be presented using the following descriptive statistics: N, mean, standard deviation, median, minimum and maximum. Continuous variables may also be presented using frequencies and percentages among appropriate categorizations. Categorical variables will be presented using frequencies and percentages. The Kaplan-Meier methodology will be used to summarize time-to-event variables. The number of patients with events and the number of censored patients will also be presented. The stratified logrank test will be used to compare the time-to-event distributions between the randomized treatment groups. In addition, the Cox proportional hazards model will be used to estimate the HR between the randomized treatment groups.

The primary and key secondary endpoints will be tested among the tBRCA and all HRD subgroups, and all randomized patients, using an ordered step-down multiple comparisons procedure. Investigator determined PFS (invPFS) in the tBRCA subgroup will be tested first at a one-sided 0.025 significance level. If invPFS in the tBRCA subgroup is statistically significant, then invPFS will be tested in the all HRD subgroup followed by invPFS in all randomized patients. Continuing in an ordered step-down manner, the PRO of disease symptoms utilizing the FOSI-18 DRS-P subscale will be tested at the one-sided 0.025 significance level in the tBRCA, all HRD, and all randomized patients subgroups and then for the remaining key secondary endpoints of PRO utilizing the FOSI-18 total score and OS. Once statistical significance is not achieved for one test the statistical significance will not be declared for all subsequent analyses in the ordered step-down procedure.

PFS by IRR will be evaluated as a stand-alone secondary endpoint.

All data will be used to their maximum possible extent but without any imputations for missing data.

All statistical analyses will be conducted with the SAS® System, v9.1 or higher.

Unless otherwise specified, baseline is defined as the last measurement on or prior to the first day of study drug administration.

### ***11.2.2 Patient Disposition***

Patient disposition (analysis population allocation, entered, discontinued, along with primary reason for discontinuation) will be summarized using frequency counts, and the corresponding percentages.

### ***11.2.3 Baseline Characteristics***

All demographic and baseline characteristics will be summarized for the safety population.

The following variables will be summarized with frequency tabulations:

- Time since diagnosis (months): > 12-24, > 24
- Baseline laboratory parameters: graded based on CTCAE
- HRD status for stratification at randomization: tBRCA, nbHRD, biomarker negative
- Interval between completion of penultimate platinum regimen and disease progression (6 to 12 months or >12 months) by radiologic assessment
- Best response to most recent platinum-based regimen (CR [defined as complete radiologic response by RECIST v1.1 with normalization of CA-125] or PR [defined as partial radiologic response by RECIST v1.1 and/or a GCIG CA-125 response]). All responses require that CA-125 be <ULN.

Descriptive statistics may also be used to summarize the continuous variables.

### ***11.2.4 Efficacy Analyses***

All efficacy evaluations will be conducted using the ITT population.

#### **11.2.4.1 Primary Efficacy Analysis**

The primary efficacy endpoint for the study is invPFS by RECIST v1.1. Investigator-determined PFS is defined as the time from randomization to disease progression, according to RECIST v1.1 criteria ([Appendix B](#)), as assessed by the investigator, or death due to any cause, in molecularly defined subgroups. The stratification factors included in the primary analysis of invPFS will be as follows:

- HRD classification (tBRCA or nbHRD or biomarker negative)
- Interval between completion of penultimate platinum regimen and disease progression (6 to 12 months or >12 months) by radiologic assessment
- Best response to the most recent platinum-based regimen (CR [defined as complete radiologic response by RECIST v1.1 with normalization of CA-125] or PR [defined as partial response by RECIST v1.1 and/or a GCIG CA-125 response]). All responses required that CA-125 be <ULN.

Tumor HRD status by the FCTA will be determined after randomization, but before the final efficacy analysis, so that the primary endpoint (PFS in molecularly-defined HRD subgroups) can be assessed prospectively.

#### **11.2.4.2 Secondary Efficacy Analyses**

Secondary efficacy endpoints are:

- Time to a 4-point decrease in the FOSI-18 DRS–P subscale
- Time to an 8-point decrease in the FOSI-18 total score
- OS
- PFS by RECIST v1.1 as assessed by IRR (irrPFS)

##### ***PRO of disease-related symptoms as measured by the FOSI-18 DRS–P subscale***

The time to an event in PRO of worsening of disease symptoms will be defined as the time from randomization to a 4-point reduction in the FOSI-18 DRS-P subscale. Patients without a 4-point reduction will be censored on the date of their last PRO evaluation.

##### ***PRO as measured by the total score of the FOSI-18***

An event in worsening of PRO utilizing the complete FOSI-18 instrument will be defined as the time from randomization to an 8-point reduction in the total score. Patients without an 8-point reduction will be censored on the date of their last PRO evaluation.

##### ***Overall survival***

Overall survival (OS) is defined as the number of days from the date of randomization to the date of death (due to any cause). Patients without a known date of death will be censored on the date the patient was last known to be alive.

An interim OS was determined at the time of the primary endpoint unblinding ([Section 11.3](#)). The final OS analysis will be performed at the time of the study close. See [Section 11.3](#) for further details.

##### **irrPFS**

PFS for secondary efficacy analysis is defined as the time from randomization to disease progression, according to RECIST v1.1 criteria as assessed by IRR, or death due to any cause, whichever occurs first.

#### **11.2.5 Safety Analyses**

Safety endpoints are incidence of AEs, clinical laboratory abnormalities, and dose modifications.

Data from all patients who receive at least one dose of study drug will be included in the safety analyses. AEs, clinical laboratory information, vital signs, ECG results, ECOG performance status, body weight, and concomitant medications/procedures will be tabulated and summarized.

#### **11.2.5.1 Adverse Events**

AEs will be classified using the Medical Dictionary for Drug Regulatory Activities (MedDRA) classification system. The severity of the toxicities will be graded according to the NCI-CTCAE whenever possible. Only treatment-emergent adverse events (TEAEs) will be collected: TEAEs are defined as AEs with onset date on or after the date of first dose of study medication until the date of the last study medication dose plus 28 days.

The number and percentage of patients who experienced TEAEs for each system organ class (SOC) and preferred term will be presented. Multiple instances of the TEAE in each SOC and multiple occurrences of the same preferred term are counted only once per patient. The number and percentage of patients with at least one TEAE will also be summarized.

Separate tables will be presented as follows:

- All TEAEs
- TEAEs by CTCAE grade
- Grade 3 or greater TEAEs
- Serious TEAEs
- TEAEs with an outcome of death
- TEAEs leading to discontinuation of study medication
- TEAEs resulting in interruption/delay of study medication
- TEAEs resulting in dose reduction of study medication

If a patient experiences multiple occurrences of the same AE with different toxicity grades, the patient will be counted once for the maximum (most severe) toxicity grade. AEs with a missing toxicity grade will be presented in the summary table with a toxicity grade of "Missing." For each toxicity grade, the number and percentage of patients with at least one TEAE of the given grade will be summarized.

#### **11.2.5.2 Clinical Laboratory Evaluations**

Clinical laboratory evaluations include the continuous variables for hematology, serum chemistry, and urinalysis. The laboratory values will be presented in SI units. The on-treatment period will be defined as the time from the first dose of study drug to 28 days after the last dose of study drug. Laboratory values collected during the on-treatment period will be included in the summary tables. The laboratory values collected after the on-treatment period will only be presented in the data listings.

The summary of laboratory data will include shift tables based on CTCAE for shifts in grade from baseline to maximum, minimum and last value during the on-treatment period.

Supporting laboratory data including normal ranges and abnormal laboratory flags will be provided using by-patient listings. Separate listings will be produced for clinically significant laboratory abnormalities (i.e. those that meet Grade 3 or 4 criteria according to CTCAE).

### **11.2.5.3 Vital Sign Measurements**

The on-treatment period will be defined as the time from the first dose of study drug to 28 days after the last dose of study drug. Vital sign measurements collected during the on-treatment period will be included in the summary tables. The vital sign measurements collected after the on-treatment period will only be presented in the data listings.

The summary of vital sign data will include descriptive statistics (N, mean, SD, minimum, median, third quartile and maximum) of the maximum, minimum and last value during the on-treatment period. Summaries using descriptive statistics (N, mean, SD, minimum, median and maximum) of the change from baseline to the maximum, minimum, and last value during the on-treatment period will also be given.

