12.2 Clinical Laboratory Evaluations

Clinical laboratory evaluations include the continuous variables for hematology, serum chemistry, and urinalysis. The laboratory values will be presented in SI units. The on-treatment period will be defined as the time from randomization to 28 days after the last dose of study drug. Laboratory values collected during the on-treatment period will be included in the summary tables. The laboratory values collected after the on-treatment period will only be presented in the data listings.

The summary of laboratory data will include descriptive statistics (N, mean, SD, minimum, median, and maximum) of the maximum, minimum, and last value during the on-treatment period. Summaries using descriptive statistics of the change from baseline to the maximum, minimum, and last value during the on-treatment period will also be given.

Summary tables from baseline to the maximum on-treatment toxicity grade (CTCAE Version 4.03) for each lab parameter will be summarized. In addition, the number and percent of patients who has at least one worsening in toxicity grade on-treatment compared to baseline toxicity grade will be summarized by treatment group.

Laboratory data including normal ranges and flagged abnormal laboratory findings will be provided using by-patient listings.

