12.3 Vital Signs

The on-treatment period will be defined as the time from randomization to 28 days after the last dose of study drug. Vital sign measurements collected during the on-treatment period will be included in the summary tables. The vital sign measurements collected after the on-treatment period will only be presented in the data listings.

The summary of vital sign data will include descriptive statistics (N, mean, SD, minimum, median, third quartile and maximum) of the maximum, minimum and last value during the on-treatment period. Summaries using descriptive statistics (N, mean, SD, minimum, median, and maximum) of the change from baseline to the maximum, minimum, and last value during the on-treatment period will also be given. The data will be presented separately for each randomized treatment group, and overall.

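### Vital-sign and continuous laboratory tables rest on whole-treatment extremes, which depend on time on drug; a by-visit table is needed to compare the arms

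*Protocol*

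**What the plan says.** Protocol 11.2.5.3 plans descriptive statistics for vital signs on each patient's maximum, minimum and last on-treatment value, and on the "change from baseline to the maximum, minimum, and last value during the on-treatment period". SAP 12.3 repeats this and presents the result by randomized arm.

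For laboratory data the two documents differ. Protocol 11.2.5.2 plans CTCAE tables of "shifts in grade from baseline to maximum, minimum and last value during the on-treatment period". SAP 12.2 adds continuous summaries ("N, mean, SD, minimum, median, and maximum) of the maximum, minimum, and last value during the on-treatment period") and then: "Summaries using descriptive statistics of the change from baseline to the maximum, minimum, and last value during the on-treatment period will also be given". It also counts patients with "at least one worsening in toxicity grade on-treatment compared to baseline toxicity grade".

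The window is patient-specific. In Protocol 11.2.5.3 it is the "time from the first dose of study drug to 28 days after the last dose of study drug". SAP 12.3 starts it elsewhere: "The on-treatment period will be defined as the time from randomization to 28 days after the last dose of study drug". Both end at the same point.

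These sections contain no by-visit table, common window, count of readings or adjustment for exposure. By contrast, change from baseline in CA-125 and EQ-5D is planned for each scheduled visit (Protocol 11.2.7.1 and 11.2.7.5; SAP 10.4.1 and 10.4.6).

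**The concern.** A patient's maximum depends on how many readings were taken as well as on the level of the measure. With a constant level and ordinary fluctuation, more readings give a higher expected maximum and a lower expected minimum. Treatment continues to progression, and the sample-size tables assume later progression on rucaparib. The arm expected to stay on drug longer therefore contributes more readings per patient.

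The shift lies in the chosen statistic. A mean of maxima is not a rate, so dividing by person-time would not remove it, and the separate tabulation of treatment duration (SAP 7) does not correct it.

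What is at stake is how the tables are read. They are the only vital-sign summaries and the only continuous laboratory summaries planned. A higher mean change to maximum on rucaparib could be taken for a drug effect when it reflects longer observation. SAP 12.4 repeats the safety analyses in tBRCA and HRD, where the assumed exposure gap is widest.

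**Working it through.** **Plan's own figure first.** The documents give no figure for the extremes. The input is the assumed median PFS, so I checked the ITT row of the power table (Protocol Table 4; SAP 2.3). Events: 0.70 × 540 = 378. Median ratio: 6/8.5 = 0.706, against a stated HR of 0.70. Power by Schoenfeld's formula with 2:1 allocation: √(378 × 2/3 × 1/3) × |ln 0.70| − 1.96 = 9.165 × 0.3567 − 1.96 = 1.31, which gives 90.5% (stated 90%).

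**Inputs from the documents.** Median PFS for placebo against rucaparib: 6 vs 8.5 (ITT), 6 vs 10 (HRD) and 6 vs 12 months (tBRCA). Cycles of 28 days, scans every 12 weeks, 30.4375 days per month.

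**Assumptions.** PFS stands in for time on treatment and is exponential. There is one reading per cycle plus one at discontinuation. Data cut-off is 12 months, 24 months or none. Treatment stops at the event or at the next 12-weekly scan. Readings are normal with within-patient SD 1, autocorrelation 0, 0.5 or 0.8, no drug effect and no time trend.

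**Mechanism at the median patient.** Readings n = floor(months × 30.4375/28) + 1.

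- 6 months: 182.6/28 = 6.5, n = 7
- 8.5 months: 258.7/28 = 9.2, n = 10
- 12 months: 365.25/28 = 13.04, n = 14

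For n independent standard normal readings, E[max] = ∫ x·n·φ(x)·Φ(x)^(n−1) dx, which is 1.352, 1.539 and 1.703. The gaps are 1.539 − 1.352 = 0.19 SD and 1.703 − 1.352 = 0.35 SD, with the mirror image at the minimum.

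**Averaged over patients (null simulation; differences taken before rounding).**

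| Setting (scan-timed stopping) | Medians | Mean readings | Change to max, placebo / rucaparib (diff.) | Change to min (diff.) | Last value (diff.) |
|---|---|---|---|---|---|
| 24-month cut-off, independent | 6 vs 8.5 | 11.3 / 13.8 | 1.47 / 1.58 (+0.11) | −1.48 / −1.57 (−0.09) | 0.00 |
| 24-month cut-off, independent | 6 vs 10 | 11.3 / 14.9 | 1.47 / 1.62 (+0.14) | −1.48 / −1.61 (−0.13) | +0.01 |
| 24-month cut-off, independent | 6 vs 12 | 11.3 / 16.2 | 1.47 / 1.66 (+0.20) | −1.48 / −1.66 (−0.18) | +0.01 |
| 12-month cut-off, autocorrelation 0.8 | 6 vs 8.5 | 9.2 / 10.2 | 0.93 / 0.98 (+0.05) | −0.93 / −1.00 (−0.07) | −0.01 |
| 12-month cut-off, autocorrelation 0.8 | 6 vs 12 | 9.2 / 11.1 | 0.93 / 1.04 (+0.11) | −0.93 / −1.05 (−0.12) | −0.01 |

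Over all settings the shift at the maximum is +0.05 to +0.17 SD (6 vs 8.5 months) and +0.11 to +0.34 SD (6 vs 12 months), with a near mirror image at the minimum. The upper ends come from no cut-off and stopping at the event itself.

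**In units.** If the within-patient systolic SD is 8-12 mmHg (assumed), 0.05 × 8 = 0.4 to 0.17 × 12 = 2.0 mmHg at the ITT medians, and 0.11 × 8 = 0.9 to 0.34 × 12 = 4.1 mmHg at the tBRCA medians.

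**Any-worsening count.** With an assumed 5% chance per reading of crossing a grade threshold, the chance of at least one crossing is 1 − 0.95^n. Averaged over patients (24-month cut-off, scan-timed) this is 40% vs 47% (6 vs 8.5 months) and 40% vs 52% (6 vs 12). The SAP's worsening table shares the dependence.

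**Checks on the cause.** With equal medians the difference is 0. With rucaparib at 5 against 6 months it reverses, to about −0.05 SD at the maximum. Restricted to each patient's first three readings, both arms give +0.85 and −0.85 SD, a difference of 0.00.

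**The case against.** **No test is planned.** These tables are descriptive. A reader might infer a false-positive rate from the simulation, where a nominal 95% interval excludes zero in a given direction in 14-28% of null trials. The plan contains no such interval or test, so no formal error rate applies. This stands.

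**The shift is an average.** A reader might infer that rucaparib will seem to raise and lower every measure at once. At the planned arm sizes (24-month cut-off, independent readings), point estimates go both ways in 63-81% of null cases per measure, and nominal intervals exclude zero in both directions in only 0.1-3%. It also needs longer rucaparib exposure, which is a design assumption. This stands.

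**The same table holds the last value.** Its null arm difference is about zero, so it should not be called biased by the number of readings. It is, however, read at different times in the two arms, so it does not give a comparison at equal time on study.

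**Safety conclusions rest elsewhere.** Protocol 11.2.5 names AEs, laboratory abnormalities and dose modifications as the safety endpoints; vital signs are not among them. Grade shifts, listings and AE tables cover laboratory abnormalities, and the Protocol itself plans no continuous laboratory extremes. It would go too far to say that the safety analysis cannot support conclusions.

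**Extremes have a use.** Protocol 3.3.2.1.1 notes that myelosuppression can appear late. Confining extremes to early cycles would drop late nadirs from the continuous tables. That argues for adding a table and keeping the existing ones.

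**Conclusion.** The point holds as a limited one about descriptive tables. If time on rucaparib is longer, as the design assumes, mean change to maximum is expected to be higher and mean change to minimum lower on rucaparib with no drug effect: roughly 0.05-0.17 within-patient SD at the ITT medians and 0.11-0.34 SD at the tBRCA medians. The direction follows from the unequal number of readings. The size rests on assumed monthly readings, follow-up, autocorrelation and PFS as a proxy for time on treatment, and the shift would shrink or reverse if rucaparib exposure were not longer. For laboratory values, the continuous form of the problem is in the SAP only. The primary efficacy analysis is untouched.

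**What to change.** In Protocol 11.2.5.3 and SAP 12.2 and 12.3:

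1. Keep the whole-treatment maximum, minimum and last value, for outliers and late toxicity.
2. Add a by-arm table of change from baseline at each scheduled visit where readings were collected, with the number observed, as already planned for CA-125 and EQ-5D.
3. Report the number of readings per patient by arm beside the extremes.
4. State that arm differences in the extremes are not to be read as drug effects.
5. Reconcile the start of the on-treatment window (first dose in the Protocol, randomization in the SAP).

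The cost is wording and a few extra tables from data already collected. Protocol 11.3 says that all endpoints were summarized when the primary endpoint was unblinded, so this would be a re-tabulation. After Amendment 5 vital signs follow local practice (Protocol 9.5.4.4) and the eCRF list in 13.6 has no vital-sign or laboratory form, so the table covers only visits with recorded data. Later visits include only patients still on treatment, which is why the number observed must be shown.
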